# 2.6.3 Handling of intercurrent events

Though no secondary estimands are defined for the study, intercurrent events defined in the primary estimands will impact secondary endpoints analysis. Thus they will be handled in the same way as in primary estimands analyses. Participants who receive the investigational imaging agent [18F]CTT1057 but do not undergo/complete the PET/CT scan for any reasons (e.g. consent withdrawal, PET camera failures, etc.) will not be used for the secondary efficacy endpoint analyses, but safety data for these participants will be collected after the administration of the investigational imaging agent and will be summarized.

### 2.6.4 Handling of missing values not related to intercurrent event

This is a diagnostic study, where the secondary endpoints are calculated on the basis of a one-time imaging assessment. Missing data will not be imputed.

## 2.6.5 Sensitivity analyses

No sensitivity analyses are planned for the secondary endpoints.

### 2.6.6 Supplementary analyses

Supplementary analyses for patient-level and region-level diagnostic performance parameters defined in Section 2.6.2 will be performed for the following subgroup:

- PSA level at baseline (from central laboratory):
  - $\circ$  PSA  $\leq 0.5$  ng/mL
  - $\circ$  0.5 ng/mL<PSA $\leq$ 1 ng/mL
  - $\circ$  1 ng/mL<PSA $\leq$ 2 ng/mL
  - o 2 ng/mL<PSA≤5 ng/mL
  - $\circ$  PSA > 5 ng/mL

# 2.7 Safety analyses

Safety summaries (tables, figures) include only data from the on-treatment period with the exception of baseline data which will also be summarized where appropriate (e.g. change from baseline summaries). Safety summary tables will be presented using the F-SAF and Ga-SAF separately, and listings will be provided for the SAF, unless otherwise specified.

The overall observation period will be divided into three mutually exclusive segments (see Section 2.1.1 for details).

### 2.7.1 Adverse events (AEs)

Adverse events are coded using MedDRA terminology. The latest MedDRA version used for reporting will be specified in the CSR and as a footnote in the applicable tables/listings. AEs will be assessed according to the Common Terminology Criteria for Adverse Events (CTCAE) version 5.0. Summary tables for adverse events (AEs) will include only AEs that started or worsened during the on-treatment period (see Section 2.1.1). All AEs that started or worsened within 14 days after the [F]CTT1057 dose and as long as they were prior to the [Ga]Ga-

PSMA-11 dose (applicable for Sequence 1), and adverse events that were reported as related to [F]CTT1057 irrespective of time of onset will be regarded as [F]CTT1057 **treatment-emergent** AEs. Similarly, all AEs that started or worsened within 14 days after the [Ga]Ga-PSMA-11 dose and as long as they were prior to the [F]CTT1057 dose (applicable for Sequence 2), and adverse events that were reported as related to [Ga]Ga-PSMA-11 irrespective of time of onset will be regarded as [Ga]Ga-PSMA-11 **treatment-emergent** AEs. [F]CTT1057 TEAEs and [Ga]Ga-PSMA-11 TEAEs will be summarized.

AEs will be summarized by the number and percentage of participants having at least one AE, having at least one AE in each primary system organ class (SOC) and for each preferred term (PT) using MedDRA coding. A participant with multiple occurrences of an AE will be counted only once in the respective AE category. A participant with multiple CTCAE grades for the same preferred term will be summarized under the maximum CTCAE grade recorded for the event. AE with missing CTCAE grade will be included in the 'All grades' column of the summary tables.

In AE summaries, the primary system organ class will be presented alphabetically and the preferred terms will be sorted within primary SOC in descending frequency.

The following adverse event summaries will be produced: overview of adverse events and deaths (number and % of participants who died, with any AE, any SAE, any dose change, drug withdrawn etc.), AEs by SOC, PT and maximum grade, by relationship (all AEs and AEs related to study treatment), seriousness (SAEs and non-SAEs), leading to treatment discontinuation, leading to dose change, requiring additional therapy, and leading to fatal outcome. In addition, a summary of serious adverse events with number of occurrences will be produced (an occurrence is defined as >1 day between start and prior end date of record of same preferred term). To help evaluate the impact of the COVID-19 on the safety, the incidence of COVID-19 related adverse event preferred terms will be presented. All COVID-related AEs will be included in the listings.

For the legal requirements of ClinicalTrials.gov and EudraCT, two required tables for ontreatment emergent adverse events which are not serious adverse events with an incidence of greater than 5% and on-treatment emergent serious adverse events and SAE suspected to be related to study treatment will be provided by SOC and PT for the SAF.

If for the same participant, several consecutive AEs (irrespective of study treatment causality, seriousness and severity) occurred with the same SOC and PT:

- a single occurrence will be counted if there is ≤ 1 day gap between the end date of the preceding AE and the start date of the consecutive AE
- more than one occurrence will be counted if there is > 1 day gap between the end date of the preceding AE and the start date of the consecutive AE

For occurrence, the presence of at least one SAE / SAE suspected to be related to study treatment / non SAE has to be checked in a block e.g., among AE's in a  $\leq$  1 day gap block, if at least one SAE is occurring, then one occurrence is calculated for that SAE.

The number of deaths resulting from SAEs suspected to be related to study treatment and SAEs irrespective of study treatment relationship will be provided by SOC and PT.

All AEs collected in the AE (e)CRF page will be listed along with the information collected on those AEs, e.g. AE relationship to study drug, AE outcome, etc. All AEs, deaths, and serious adverse events (including those from the pre- and post-treatment periods) will be listed and those collected outside of the on-treatment period will be flagged.

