#### On-treatment assessment/event and observation periods

For adverse event reporting, the overall observation period will be divided into three mutually exclusive segments:

- 1. *pre-treatment period*: from day of participant's informed consent to the day/time before administration of study treatment
- 2. *on-treatment period*: from date of first administration of study treatment to 14 days after date of actual administration of any study treatment (including the administration date). The on–treatment period will be divided into the F-on-treatment period and Ga-on-treatment period for the respective study treatment of [18F]CTT1057 or [68Ga]Ga-PSMA-11
  - The F-on-treatment period is from the date of [F]CTT1057 administration to 14 days after the date of [F]CTT1057 administration.
  - The Ga-on-treatment period is from the date of [Ga]Ga-PSMA-11 administration to 14 days after the date of [Ga]Ga-PSMA-11 administration.
- 3. *post-treatment period*: starting 15 days after the date of last administration of study treatment.

Safety summaries (tables, figures) include only data from the on-treatment period with the exception of baseline data which will also be summarized where appropriate (e.g. change from baseline summaries). In addition, a separate summary for death including on-treatment and

post-treatment deaths will be provided. In particular, summary tables for adverse events (AEs) will summarize *treatment-emergent* AEs only (see Section 2.7.1).

However, all safety data (including those from the post-treatment period) will be listed and those collected during the pre-treatment and post-treatment period will be flagged.

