# 2.7.1.1 Safety topics of interest / grouping of AEs

A safety topic of interest (STI) is a grouping of adverse events that are of scientific and medical concern specific to the tracer [F]CTT1057 and [Ga]Ga-PSMA-11. These groupings are defined using MedDRA terms, SMQs (standardized MedDRA queries), HGLTs (high level group terms), HLT (high level terms) and PTs (preferred terms). Customized SMQs (Novartis MedDRA queries, NMQ) may also be used. A NMQ is a customized group of search terms which defines a medical concept for which there is no official SMQ available or the available SMQ does not completely fit the need. It may include a combination of single terms and/or an existing SMQ, narrow or broad. STI will be defined at the project level and may be regularly updated. The grouping of AEs in STI according to project standards will be specified in the electronic Case Retrieval Sheet (eCRS) for each specific tracer ([F]CTT1057 and [Ga]Ga-PSMA-11). For each specified STI, the number and percentage of participants with at least one event of the STI occurring during the on-treatment period will be summarized.

STIs will be summarized by grade, SAE, relationship, leading to treatment discontinuation, leading to dose adjustment/interruption, hospitalization, death etc. A listing of all grouping levels down to the MedDRA preferred terms used to define each STI will be generated. The analyses related to STIs for [F]CTT1057 will be carried out using the F-SAF and the analyses related to STIs for [Ga]Ga-PSMA-11 will be carried out using the Ga-SAF.

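### The SAP counts late tracer-related adverse events as treatment-emergent, but its on-treatment-only sentences and its safety-topic rule still leave them out

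*SAP*

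**What the plan says.** SAP 2.7.1 begins with a filter: "Summary tables for adverse events (AEs) will include only AEs that started or worsened during the on-treatment period". It then defines the treatment-emergent AEs (TEAEs) of each tracer in two parts. The first part is events that start or worsen within 14 days of that tracer and before the other one is given. The second part is events reported as related to the tracer, which "irrespective of time of onset will be regarded as" TEAEs of that tracer. The paragraph ends by stating that "Ga-PSMA-11 TEAEs will be summarized", and the same sentence covers [18F]CTT1057.

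SAP 2.1.1 (on-treatment assessment/event and observation periods) contains both rules. Its general sentence reads "Safety summaries (tables, figures) include only data from the on-treatment period with the exception of baseline data". Shortly afterwards it says that AE tables "will summarize *treatment-emergent* AEs only (see Section 2.7.1"). It defines an overall on-treatment period, from the first dose to 14 days after any study treatment, and says this period "will be divided into the F-on-treatment period and Ga-on-treatment period for the respective study treatment of" each tracer. SAP 2.7 repeats the general restriction: "Safety summaries (tables, figures) include only data from the on-treatment period".

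For safety topics of interest, SAP 2.7.1.1 counts participants "with at least one event of the STI occurring during the on-treatment period will be summarized". It does not mention TEAEs. Those tables are broken down by relationship, among other things, and use the F-SAF and Ga-SAF.

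**The concern.** Take a related AE with onset after the on-treatment period. The second part of the TEAE definition makes it an event to be summarized, and the opening sentence of the same section keeps it out of the tables. If a programmer applies the opening sentence as written, the wider TEAE definition has no effect on the tables. If the definition is applied instead, the AE tables include the event and the safety-topic tables do not, because 2.7.1.1 has no matching extension.

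Safety and tolerability is a stated secondary objective. Protocol 10.1.3 sends serious events more than 14 days after the last dose to sponsor safety only when the investigator suspects a causal link. The late serious events reported by that route are therefore related ones, which is the group that the literal filter removes from the tables.

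**Working it through.** No power or error-rate figure is involved. The check applies the period definitions to dates and then compares the rules on example events.

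**Inputs.** An on-treatment period ends 14 days after dosing (SAP 2.1.1). The second tracer is planned for Study Day 15-22 (SAP 2.1.1, windows for multiple assessments). Planned numbers are 190 enrolled and at least 152 evaluable (SAP 3).

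**Last included and first excluded onset day.** Last included day = dose day + 14; first excluded day = dose day + 15.

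- Overall period, either sequence, second dose on Day 15-22: last included 15 + 14 = Day 29 to 22 + 14 = Day 36; first excluded Day 30-37.
- [18F]CTT1057 period, Sequence 1, dose on Day 1: last included 1 + 14 = Day 15; first excluded Day 16.
- [18F]CTT1057 period, Sequence 2, dose on Day 15-22: last included Day 29-36; first excluded Day 30-37.

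The protocol requires only that the scans be at least 14 days apart, so a second dose after Day 22 moves the dates that depend on it later.

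**Example.** Sequence 1, [18F]CTT1057 on Day 1, [68Ga]Ga-PSMA-11 on Day 15, event reported as related to [18F]CTT1057:

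| Rule | Onset Day 20 | Onset Day 31 |
|---|---|---|
| TEAE of [18F]CTT1057 (2.7.1) | yes | yes |
| In overall on-treatment period (to Day 29) | yes | no |
| In [18F]CTT1057 period (to Day 15) | no | no |
| AE table, TEAE definition governs | in | in |
| AE table, opening sentence applied literally | depends on period | out |
| Safety-topic table (2.7.1.1) | depends on period | out |

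For the Day 31 event, no literal reading both includes it in the AE table and keeps the AE and safety-topic tables on the same events. For the Day 20 event, the answer turns on which period is meant. Sections 2.7.1 and 2.7.1.1 use the unqualified term, which 2.1.1 defines as the overall period. The tracer-specific safety sets in 2.7.1.1 point towards the tracer-specific period.

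**Size per event.** If a participant's only [18F]CTT1057 TEAE is a late related event, its inclusion or exclusion moves TEAE incidence by 1/190 = 0.53 to 1/152 = 0.66 percentage points. This assumes an F-SAF between 152 and 190. The number of such events cannot be derived from the documents.

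**The case against.** The strongest reply is that the SAP already settles the AE tables. In 2.1.1 the general sentence is followed by a specific rule for AE tables that cites 2.7.1, and 2.7.1 says the TEAEs so defined will be summarized. A specific rule with a cross-reference normally prevails over a general one. The SAP's document history (20-Dec-2023) also shows that related events beyond 14 days were added deliberately. This stands as evidence of intent. It does not remove the filter, which is the opening sentence of 2.7.1 itself and is worded as exclusive.

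A second reply is that a 14-day safety-topic table is a legitimate choice and matches the 14-day TEAE rate in SAP Table 1-1. Taken alone, that is right. The difficulty is that two tables for the same tracer and safety set, both split by relationship, can disagree about a related event without the SAP saying that they should.

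A third reply is that the affected set is very small. On the overall period, literal exclusion starts only about where the Day 29 (+3) safety visit falls. The Phase I study of 20 patients reported no tracer-related reactions, all AEs are listed with those outside the period flagged, and all deaths are tabulated for the SAF. This is correct and limits the weight of the point.

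**Conclusion.** The point holds as a minor conflict of rules in safety reporting. It rests on current SAP text; the document history is used only to show intent. It affects related AEs with onset from Day 30-37 under the overall period, or from Day 16 for [18F]CTT1057 in Sequence 1 under the tracer-specific period, both for a second dose within Day 15-22. Few are expected. Efficacy results and the success criteria are untouched.

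Four stronger inferences are not supported:

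- That late related events will certainly be missing from the AE tables. The cross-reference in 2.1.1 makes inclusion the evident intent.
- That Day 16 is the cut-off in general. It applies only on the tracer-specific reading.
- That the SAP contradicts the protocol. Protocol 12.5.2 contains both an on-treatment wording for TEAEs and one with no end date.
- That unrelated AEs arising between the two tracers should be declared as listed but not tabulated. They can fall in the overall on-treatment period, and so could enter the registry tables that 2.7.1 plans for the pooled SAF.

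**What to change.** 1. In SAP 2.1.1, SAP 2.7 and the opening sentence of 2.7.1, add after the on-treatment restriction: *except TEAEs as defined in 2.7.1*.
2. In 2.7.1.1, state that the tracer-specific safety-topic tables use the same tracer-specific TEAE flag as the AE tables.
3. Keep the 14-day TEAE rate of Table 1-1 and show related AEs with later onset in a separate row, so that the planned endpoint stays visible.

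The cost is minor rewording in four places, one shared TEAE flag per tracer and one extra table row. No new data are needed. Recording the wider definition in SAP section 4 would be useful documentation but is optional.

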# 2.7.1.1 Safety topics of interest / grouping of AEs

A safety topic of interest (STI) is a grouping of adverse events that are of scientific and medical concern specific to the tracer [F]CTT1057 and [Ga]Ga-PSMA-11. These groupings are defined using MedDRA terms, SMQs (standardized MedDRA queries), HGLTs (high level group terms), HLT (high level terms) and PTs (preferred terms). Customized SMQs (Novartis MedDRA queries, NMQ) may also be used. A NMQ is a customized group of search terms which defines a medical concept for which there is no official SMQ available or the available SMQ does not completely fit the need. It may include a combination of single terms and/or an existing SMQ, narrow or broad. STI will be defined at the project level and may be regularly updated. The grouping of AEs in STI according to project standards will be specified in the electronic Case Retrieval Sheet (eCRS) for each specific tracer ([F]CTT1057 and [Ga]Ga-PSMA-11). For each specified STI, the number and percentage of participants with at least one event of the STI occurring during the on-treatment period will be summarized.

STIs will be summarized by grade, SAE, relationship, leading to treatment discontinuation, leading to dose adjustment/interruption, hospitalization, death etc. A listing of all grouping levels down to the MedDRA preferred terms used to define each STI will be generated. The analyses related to STIs for [F]CTT1057 will be carried out using the F-SAF and the analyses related to STIs for [Ga]Ga-PSMA-11 will be carried out using the Ga-SAF.

### 2.7.2 **Deaths**

Separate summaries for on-treatment and all deaths (including post-treatment death) will be produced. On-treatment death analyses will be presented for the F-SAF and Ga-SAF separately, by system organ class and preferred term. All deaths analyses will be presented for the SAF, by system organ class, preferred term, and treatment sequence.

All deaths will be listed, and post-treatment deaths will be flagged. A separate listing of deaths prior to starting treatment will be provided for all screened participants.

# 2.7.3 Laboratory data

Laboratory data from all sources (central and local laboratories) will be combined for the analysis. The summaries will include all assessments available for the lab parameter collected prior to (baseline) and within 14 days (+ 3 day-window) after each imaging agent administration (and prior to the subsequent imaging agent administration, if applicable).

All laboratory data will be listed by participant and visit/time and if normal ranges are available, abnormalities will be flagged. Summary statistics will be provided by visit/time. Shift tables

using the low/normal/high/ (low and high) classification will be used to compare baseline to the worst on-treatment value.

Grading of laboratory values will be assigned programmatically as per National Cancer Institute (NCI) CTCAE version 5.0. The calculation of CTCAE grades will be based on the observed laboratory values only, clinical assessments will not be taken into account.

CTCAE Grade 0 will be assigned for all non-missing values not graded as 1 or higher. Grade 5 will not be used.

For laboratory tests where grades are not defined by CTCAE version 5.0, results will be categorized as low/normal/high based on laboratory normal ranges.

The following listings/summaries will be generated separately for hematology and biochemistry tests:

 Listing of all laboratory data with values flagged to show the corresponding CTCAE version 5.0 grades if applicable and the classifications relative to the laboratory normal ranges

For laboratory tests where grades are defined by CTCAE version 5.0:

- Worst post-baseline CTCAE grade (regardless of the baseline status). Each participant will be counted only once for the worst grade observed post-baseline.
- Shift tables using CTCAE version 5.0 grades to compare baseline to the worst on-treatment value

For laboratory tests where grades are not defined by CTCAE version 5.0:

• Shift tables using the low/normal/high/ (low and high) classification to compare baseline to the worst on-treatment value.

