The 2 PET imaging procedures will be done at least 14 days apart. The day of the first PET imaging agent injection will be considered study Day 1. Please refer to Section 8.3.1 for the steps that will take place on each PET imaging day.

Both visits will also be considered as the End of Treatment (EOT) visits.

Safety Checks

All treated participants will be contacted by phone within 24 to 72 hours following each PET/CT scan in order to capture potential occurring Adverse Events.

Safety Follow-up

Participants will come back to the hospital 14 days (+ 3 day window) after each PET/CT scan day, for a safety visit including vital signs, lab and urine analysis. For participants undergoing surgery, radiation therapy or initiating any antineoplastic medication (provided all CTS procedures have been completed before this initiation) prior to planned safety visit, these safety follow-up assessments will need to be performed before the surgery/radiation therapy/initiation of antineoplastic medication.

Additional Follow-up

Additional follow up period will be applicable where additional diagnostic procedures are to be performed. These may include SoC pathology, imaging or other modality disease assessments (CTS Levels 1 or 2) up to 8 weeks after [¹⁸F]CTT1057 PET/CT scan or three-month follow-up imaging (from baseline) where it is clinically required for the diagnosis of particular lesion(s).

In addition, in cases where the CTS Level 2 is not feasible/appropriate or inconclusive, and the CTS Level 3 will apply and will include the assessment of PSA levels prior to starting RT (which should commence within 8 weeks of completing [18F]CTT1057 PET/CT scan) and at approximately 90 days from last day of radiation.

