² Additional follow-up includes any SoC pathology assessment (of a biopsy/salvage surgery performed up to 8 weeks from [¹⁸F]CTT1057 PET/CT scan, CTS level 1) and/or any SoC imaging diagnostic procedures assessments (at least a high-resolution CT with contrast) performed up to 8 weeks from [¹⁸F]CTT1057 PET/CT scan for CTS level 2; If CTS level 3 is applicable for the participant (in case Levels 1 or 2 are not feasible, inconclusive or negative), the PSA levels will be assessed prior to RT,

Period	Scree	ening*					1	reatme	nt						Additional Follow-up	Study Completion
Visit Name		Random ization	PET Imaging 1 ¹				Safe ty Che ck 1	PET Imaging 2 ¹ y						Safet y Follo w-up	Additional Follow- up ²	EOS
Days	Day -28 to Day - 14	Day -28 to Day - 14	Day 1 (+7)				Day 2 to 3		Day 15 (+7)				Day 16 to 17	Day 29 (+ 3)	up to 90 days after RT	Day 29 to Follow-up end
Time (post- dose)	-	-	njecti ctio Injection/ gin Imaging /			-	Pre- Injecti on ³	Inje ctio n	Post- Injection/ Pre-Imaging	lma gin g	Post- Imaging / EOT 2	-	-	-	-	

which should commence within 8 weeks after [18F]CTT1057 PET/CT scan and after both PET/CTs are completed, and at approx. 90 days from the last day of radiation ³ Assessments done prior to starting 2nd injection will be also considered as safety follow-up 14 days after the first PET Imaging Day

⁴ Vital signs will be performed at screening, at Imaging days (pre and post-injection and then before patient discharge) and at Safety follow-up visit (Day29)

⁵ Peripheral venous blood samples will be collected at screening, PET Imaging Days pre-injection and at Safety follow-up (Day 29)

⁶ Urine sample will be collected at screening and imaging days and analyzed at the clinical site if dipstick results are abnormal

⁷ Order to be placed after randomization and based on the radiopharmaceutical that requires the longest period from order to delivery

⁸ Participant will be injected intravenously either approximately 370 MBq (range 266–407 MBq) of [¹⁸F]CTT1057 or approximately 150 MBq (range 111-185MBq) of [⁶⁸Ga]Ga-PSMA-11. flushed with 10 mL saline

after [18F]CTT1057 imaging agent injection, a CT will be obtained from vertex to mid-thighs, followed by static PET emission scan over same area starting from mid-thighs. 50-100 min after [68Ga]Ga-PSMA-11 imaging agent injection, a CT will be obtained from vertex to mid-thighs, followed by static PET emission scan over same area starting from mid-thighs.

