#### Safety Follow-up

Participants will come back to the hospital 14 days (+ 3 day window) after each PET scan day, for a safety visit including vital signs, lab and urine analysis. For participants undergoing surgery, radiation therapy or initiating any antineoplastic medication (provided all CTS procedures have been completed before this initiation) prior to planned safety visit, these safety follow-up assessments will need to be performed before the surgery/radiation therapy/initiation of antineoplastic medication.

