#### Windows for multiple assessments

In order to summarize weight, vital signs, and laboratory tests collected over time (including unscheduled visits), the assessments will be time slotted. The following general rule will be applied in creating the assessment windows: If more than one assessment is done within the same time window, the assessment performed closest to the target date will be used. If 2 assessments within a time window are equidistant from the target date, then the earlier of the 2 assessments will be used. If there are multiple assessments on the same date then the worst case value will be used. Data from all assessments (scheduled and unscheduled), including multiple assessments, will be listed.

For participants randomized into sequence 1: [18F]CTT1057 - [68Ga]Ga-PSMA-11

Time Window	Planned Visit Timing	Time Window Definition
On treatment		
Baseline for [18F]CTT1057	On or before Study Day 1*	≤ Study Day 1, and time prior to [  F]CTT1057 injection
Day 1 for [18F]CTT1057	Study Day 1	Date of [18F]CTT1057 injection
Day 15 for PET for [18F]CTT1057	Study Day 15	Study Day 15 - 22, and time prior to [  Ga]Ga-PSMA-11 injection
Baseline (Day 1) for [68Ga]Ga-PSMA-11	On or before [  Ga]Ga-PSMA-11 injection and after [  F]CTT1057 injection	≥Study Day 15 and ≤ Study Day 22, time prior to [  Ga]Ga-PSMA-11 injection
Day 1 for [  Ga]Ga- PSMA-11	On [  Ga]Ga-PSMA-11 injection	Date of [  Ga]Ga-PSMA-11 injection

\*Study Day 1 = the date of [18F]CTT1057 injection

For participants randomized into sequence 2: [68Ga]Ga-PSMA-11 - [18F]CTT1057

Time Window	Planned Visit Timing	Time Window Definition	
On treatment			
Baseline for [  Ga]Ga- PSMA-11	On or before Study Day 1*	≤ Study Day 1, and time prior to [  Ga]Ga-PSMA-11 injection	
Day 1 for [  Ga]Ga- PSMA-11	Study Day 1	Date of [  Ga]Ga-PSMA- 11injection	
Day 15 for PET for [  Ga]Ga-PSMA-11	Study Day 15	Study Day 15 - 22, time prior to [  F]CTT1057 injection	
Baseline for [18F]CTT1057	On or before [  F]CTT1057 and after [  Ga]Ga-PSMA-11	≥Study Day 15 and ≤ Study Day 22, time prior to [18F]CTT1057 injection	
Day 1 for [18F]CTT1057	On [18F]CTT1057 injection	Date of [  F]CTT1057 injection	
Day 15 for [18F]CTT1057	the date of [18F]CTT1057 injection + 14 days	Study Day 29-39	

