\*Study Day 1 = the date of [68Ga]Ga-PSMA-11 injection

For vital signs, post-injection/pre-imaging, and post-imaging assessment will be compared to the baseline (pre-injection assessment) in addition to its Day 15 assessment compared to baseline. Post-injection/pre-imaging and post-imaging will be performed on the day of imaging.

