### **Data handling**

Vital signs collected prior to (baseline), and within 14 days (+ 3 day-window) after each imaging agent administration (and prior to the subsequent imaging agent administration, if applicable) will be summarized. Values measured outside of the on-treatment period will be flagged in the listings.

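### SAP 2.7.3 and 2.7.4.2 end the first tracer's laboratory and vital-sign summaries at Study Day 18, while SAP 2.1.1 and Protocol Table 8-1 accept its follow-up through Day 22

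*SAP*

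**What the plan says.** SAP 2.7.3 defines the laboratory data that enter the summaries as those collected at baseline and "within 14 days (+ 3 day-window) after each imaging agent administration (and prior to the subsequent imaging agent administration, if applicable"). The data-handling paragraph of SAP 2.7.4.2 sets the same limit for the other assessment: "Vital signs collected prior to (baseline), and within 14 days (+ 3 day-window) after each imaging agent administration".

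SAP 2.1.1 sets time slots for summarising weight, vital signs and laboratory tests. In sequence 1, the Day 15 slot for [18F]CTT1057 is "Study Day 15 - 22, and time prior to" the [68Ga]Ga-PSMA-11 injection. Sequence 2 has the mirror-image slot for [68Ga]Ga-PSMA-11. For vital signs, 2.1.1 also asks for same-day changes from baseline "in addition to its Day 15 assessment compared to baseline".

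Protocol Table 8-1 puts the second PET visit at Day 15 (+7). Footnote 3 says: "Assessments done prior to starting 2nd injection will be also considered as safety follow-up 14 days after the first PET Imaging Day". Footnote 5 lists the blood draws: "Peripheral venous blood samples will be collected at screening, PET Imaging Days pre-injection and at Safety follow-up (Day 29"). The table schedules no separate draw between the two PET days.

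Protocol Section 3 is worded differently: "Participants will come back to the hospital 14 days (+ 3 day window) after each PET/CT scan day". SAP 1.1 repeats this almost word for word: "Participants will come back to the hospital 14 days (+ 3 day window) after each PET scan day".

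**The concern.** Two parts of the SAP treat the same value differently. A pre-second-injection sample taken on Day 19-22 complies with Table 8-1, is first-tracer follow-up under footnote 3 and has a first-tracer slot in 2.1.1. It is also later than the limit in 2.7.3 and 2.7.4.2.

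This matters most for laboratory data. Under Table 8-1, the draw before the second injection is the only scheduled blood sample between the two tracers. If it is not counted and no other sample exists, the participant has no post-dose laboratory value for the first tracer. In sequence 1 that tracer is [18F]CTT1057, whose safety is a stated secondary objective. In sequence 2 it is [68Ga]Ga-PSMA-11. The denominators of the first-tracer tables would then depend on which paragraph the programmer follows.

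**Working it through.** **Inputs.** Study Day 1 is the day of the first injection (Protocol Section 3), and a later study day is the date difference plus 1 (SAP 2.1.1). The second PET visit is on Day 15 to 22 (Table 8-1). The summary limit is 14 (+3) days after administration (SAP 2.7.3 and 2.7.4.2).

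**Reproducing a stated window.** For sequence 2, SAP 2.1.1 slots the second tracer's Day 15 assessment at Study Day 29-39. A second injection on Day 15 to 22, followed by 14 (+3) days, gives:
- earliest: 15 + 14 = 29
- latest: 22 + 14 + 3 = 39

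This matches, so 14 (+3) means 14 to 17 days after injection, and the second tracer's rules agree with each other.

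**First tracer, injected on Study Day 1.**
- Limit in 2.7.3 and 2.7.4.2: 1 + 14 + 3 = Study Day 18.
- Slot in 2.1.1 and Table 8-1: Study Day 15 to 22, which is 8 permitted days, 14 to 21 days after injection.
- Accepted by the slot but beyond the limit: Study Days 19, 20, 21 and 22, which is 4 of the 8 days, 18 to 21 days after injection.

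**A pre-second-injection value on Day 20 (19 days after the first tracer).**

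| First-tracer output | SAP 2.1.1 | SAP 2.7.3 / 2.7.4.2 | Result |
|---|---|---|---|
| Laboratory shift and worst-grade tables | not a by-visit slot | beyond 17 days | out; participant absent if no other sample |
| By-visit laboratory summary | in slot | beyond 17 days | conflict |
| Day 15 vital-sign change from baseline | in slot | beyond 17 days | conflict |
| Same-day post-injection and post-imaging vital signs | in | in | kept |
| Listings | not restricted | all values listed | kept |

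**Size.** Safety tables cover all dosed participants, so the base is at most about 190 / 2 = 95 per sequence. The documents give no distribution of scan intervals. As a scale only, each 1% of second scans falling on Day 19-22 is 0.01 x 95 = 0.95, about one participant per sequence. Even that is an upper count, because another sample by Day 18 would supply a value.

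**The case against.** The strongest reply is that 2.7.3 follows the body of the protocol. Section 3 and SAP 1.1 can be read as requiring a visit 14 (+3) days after each scan. On that reading, a participant scanned on Day 19-22 should already have a sample by Day 18, and nothing is lost. Footnote 3 says the pre-injection assessments also count as follow-up, not that they replace such a visit. This reading is fair, and part of the cause is in the protocol. But Table 8-1 and footnote 5 schedule no such visit or draw, and 2.1.1 and 2.7.3 would still disagree.

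A second reply is that 2.7.3 says what the summaries include and never says only. It adds that the overall on-treatment period in 2.1.1 runs to 14 days after any study treatment, so it could cover Day 19-22. A stated window is naturally read as a limit, however. The overall period also does not govern tables produced per tracer on F-SAF and Ga-SAF, and the tracer-specific periods, introduced for adverse event reporting, stop at 14 days.

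The reply on vital signs stands in part. A reader might infer that a late-scanned participant certainly drops out of the Day 15 vital-sign comparison. The documents do not support that: 2.1.1 prescribes the comparison and gives it a slot through Day 22. What can be said is that precedence is not stated.

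It is also fair that safety is otherwise framed on 14 days and that stopping at 17 days is defensible on attribution grounds. That supports choosing one rule and saying so; it does not support leaving two.

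**Conclusion.** The inconsistency is real and minor. For the first tracer, the summary limit (Study Day 18) and the accepted follow-up window (Study Day 22) differ by four days. Applying 2.7.3 takes a participant with a Day 19-22 second scan, and no other sample by Day 18, out of the first-tracer laboratory shift and worst-grade tables. For the by-visit laboratory summaries and the Day 15 vital-sign comparison, the finding is a conflict without a stated precedence, not a certain loss.

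A reader might take 4 of 8 days to mean that half the participants are affected. It is a count of permitted days, not a probability. Protocol 6.1.5 plans the second injection for approximately Day 15, so the number is probably small.

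Nor would the data disappear. All laboratory values are listed with CTCAE grades flagged where applicable, same-day vital signs are summarised, and the late value still serves as the second tracer's baseline. The second tracer's follow-up window is consistent, and no efficacy analysis is involved. The conclusion assumes that sites follow Table 8-1 where it differs from Section 3 and that the programmer reads 2.7.3 as a limit.

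**What to change.** In SAP 2.7.3 and 2.7.4.2, count the pre-second-injection assessment as the first tracer's post-dose value through Study Day 22, as 2.1.1 and footnote 3 already do. State that it enters the laboratory shift and worst-grade tables, which also settles which window the worst on-treatment value refers to. Where a sample within 14 (+3) days also exists, keep it as the by-visit Day 15 value under the closest-to-target rule in 2.1.1. Report how many values were taken more than 17 days after dosing. The interval summary already planned in SAP 2.4.1 will show how many second scans were late.

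The cost is SAP wording and window programming, with no new assessments. The downside is that values 18 to 21 days after a single tracer dose are harder to attribute to it, which is why the count beyond 17 days should be reported.
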